Week 7 of DiAs Use in Phase 3 Mode	Technology Acceptance (burdens subscale only) to assess patients' experienced burdens related to the use of DSS Pittsburgh Sleep Quality Index (PSQI) to assess whether DSS improves sleep quality and quantity.	Pittsburgh Sleep Quality Index T1-Diabetes Distress Scale
Week 8 of DiAs Use in Phase 3 Mode	Hypoglycemia Fear Survey Hyperglycemia Avoidance Confidence in Diabetes Self-Care Scale	Hypoglycemia Fear Survey Hyperglycemia Avoidance Scale Confidence in Diabetes Self-Care Scale
Visit 6 Study Exit	ABACUS INSPIRE (revised for DSS) Diabetes Locus of Control	ABACUS

1285

1286 **Chapter 10 Risks, Benefits, and Risk Assessment**

1287 **10.1. Potential Risks and Benefits of the Investigational Device**

1288 Risks and Benefits are detailed below. Loss of confidentiality is a potential risk; however, data are
1289 handled to minimize this risk. Hypoglycemia, hyperglycemia and ketone formation are always a
1290 risk in participants with T1DM and participants will be monitored for these symptoms.

1291 **10.1.1. Venipuncture Risks**

1292 A hollow needle will be placed in the arm for taking blood samples. Blood draws can cause some
1293 common reactions like pain, bruising, or redness at the sampling site. Less common reactions
1294 include bleeding from the sampling site, formation of a small blood clot or swelling of the vein
1295 and surrounding tissues, and fainting.

1296 There is the risk of contamination from blood sampling techniques. Hand washing with either
1297 soap & water or waterless hand sanitizer will be used prior to caring for the study subject. Gloves
1298 will be worn during blood sample collection and processing. Medical personnel will continue to
1299 practice hygiene for the subject's protection (i.e. hand washing, changing gloves frequently,
1300 disposing needles properly). Gloves will be removed and hands washed or sanitized prior to
1301 leaving and upon return to the subject's room. Soiled linen will be changed to minimize the
1302 transfer of pathogenic organisms.

1303 **10.1.2. Fingertick Risks**

1304 About 2 drop of blood will be removed by fingertick for measuring blood sugars and sometimes
1305 HbA1c or other tests. This is a standard method used to obtain blood for routine hospital
1306 laboratory tests. Pain is common at the time of lancing. In about 1 in 10 cases, a small amount of
1307 bleeding under the skin will produce a bruise. A small scar may persist for several weeks. The risk

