1394 such as a bit of liquid soap with warm water will be used. A soft towel will be used to dry the
1395 pump.

1396 Equipment that touches intact skin will be cleaned with ethyl or isopropyl alcohol (70-90%),
1397 quaternary ammonium germicidal detergent (i.e. Cavicide, EPA number 46781) or household
1398 bleach. The contact time on the surface depends on the method used to clean the equipment.
1399 Cavicide requires three minutes on the surface of the equipment. Clorox Germicidal Bleach Wipes
1400 require two minutes on the equipment. The surface should remain wet (i.e. slightly damp) with
1401 the disinfectant to be considered effective though not wet enough to leave drops of liquid.

1402 In the event a manufacturer update for cleaning procedures of their device, the study team will
1403 adhere to the most current recommendations.

1404 **Chapter 12 Adverse Events, Device Issues, and Stopping Rules**

1405 The protocol is considered a significant risk device study due to the fact that the closed loop
1406 system is experimental. Therefore, an investigational device exemption (IDE) from the U.S. Food
1407 and Drug Administration (FDA) is required to conduct the study.

1408 **12.1. Definitions**

1409 **12.1.1. Adverse Events (AE)**

1410 A reportable adverse event includes any untoward medical occurrence that meets one of the
1411 following criteria:

- 1412 • A Serious Adverse Event as defined in section 12.1.2
- 1413 • An Adverse Device Effect as defined in section 12.1.4, unless excluded from reporting in
1414 section 12.8
- 1415 • An Adverse Event as defined in section 12.1.4 occurring in association with a study
1416 procedure
- 1417 • An AE as defined in section 12.1.1 which leads to discontinuation of a study device for 2
1418 or more hours
- 1419 • Hypoglycemia meeting the definition of severe hypoglycemia as defined in section 12.3.1
- 1420 • Diabetic ketoacidosis (DKA) as defined in section 12.3.2 or in the absence of DKA, a
1421 hyperglycemic or ketosis event meeting the criteria defined below

1422 Hypoglycemia and hyperglycemia not meeting the criteria below will not be recorded as adverse
1423 events unless associated with an Adverse Device Effect. Skin reactions from sensor placement
1424 are only reportable if severe and/or required treatment.

1425 **12.1.2. Serious Adverse Event (SAE)**

1426 Any untoward medical occurrence that:

- 1427 • Results in death.

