- 1428 • Is life-threatening; (a non-life-threatening event which, had it been more severe, might
1429 have become life-threatening, is not necessarily considered a serious adverse event).
- 1430 • Requires inpatient hospitalization or prolongation of existing hospitalization.
- 1431 • Results in persistent or significant disability/incapacity or substantial disruption of the
1432 ability to conduct normal life functions (life threatening).
- 1433 • Is a congenital anomaly or birth defect.

CLINICAL PROTOCOL

- 1434 • Is considered a significant medical event by the investigator based on medical judgment
1435 (e.g., may jeopardize the participant or may require medical/surgical intervention to
1436 prevent one of the outcomes listed above).

1437 **12.1.3. Unanticipated Adverse Device Effect (UADE)**

1438 Any serious adverse effect on health or safety or any life-threatening problem or death caused
1439 by, or associated with a device, if that effect, problem, or death was not previously identified in
1440 nature, severity, or degree of incidence in the investigational plan or application (including a
1441 supplementary plan or application), or any other unanticipated serious problem associated with
1442 a device that relates to the rights, safety, or welfare of participants (21 CFR 812.3(s)).

1443 **12.1.4. Adverse Device Effect (ADE)**

1444 Any untoward medical occurrence in a study participant which the device may have caused or to
1445 which the device may have contributed.

1446 **12.1.5. Device Complaints and Malfunctions**

1447 A device complication or complaint is something that happens to a device or related to device
1448 performance, whereas an adverse event happens to a participant. A device complaint may occur
1449 independently from an AE, or along with an AE. An AE may occur without a device complaint or
1450 there may be an AE related to a device complaint. A device malfunction is any failure of a device
1451 to meet its performance specifications or otherwise perform as intended. Performance
1452 specifications include all claims made in the labeling for the device. The intended performance
1453 of a device refers to the intended use for which the device is labeled or marketed. (21 CFR 803.3).

1454 **12.2. Protocol Deviations**

1455 A protocol deviation is any noncompliance with the clinical trial protocol, Good Clinical Practices
1456 (GCP), or procedure requirements. The noncompliance may be either on the part of the

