1552 contacted for re-evaluation. If the adverse event has not resolved, additional follow-up will be
1553 performed as appropriate. Every effort should be made by the Investigator or delegate to contact
1554 the participant until the adverse event has resolved or stabilized.

1555 **12.8. Reportable Device Issues**

1556 All UADEs, ADEs, device complaints, and device malfunctions will be reported irrespective of
1557 whether an adverse event occurred, except in the following circumstances.

1558 The following device issues are anticipated and will not be reported but will reported as an
1559 Adverse Event if the criteria for AE reporting described above are met:

- 1560 • Component disconnections
- 1561 • CGM sensors lasting fewer than the number of days expected per CGM labeling
- 1562 • CGM tape adherence issues

CLINICAL PROTOCOL

- 1563 • Pump infusion set occlusion not leading to ketosis
- 1564 • Battery lifespan deficiency due to inadequate charging or extensive wireless
1565 communication
- 1566 • Intermittent device component disconnections/communication failures not leading to
1567 system replacement
- 1568 • Device issues clearly addressed in the user guide manual that do not require additional
1569 troubleshooting
- 1570 • Skin reactions from CGM sensor placement or pump infusion set placement that do not
1571 meet criteria for AE reporting

1572 **12.9. Timing of Event Reporting**

- 1573 • UADEs must be reported within 10 working days to the FDA after the sponsor first
1574 receives notice of the adverse effect.
- 1575 • Other reportable adverse events, device malfunctions (with or without an adverse event)
1576 and device complaints should be reported promptly, but there is no formal required
1577 reporting period.
- 1578 • The IDE Sponsor will investigate the UADE and if indicated, report the results of the
1579 investigation to the IRBs, FDA, and DSMB will within 10 working days of the study team
1580 becoming aware of the UADE per 21CFR 812.46(b).
- 1581 • The DSMB will determine if the UADE presents an unreasonable risk to participants. If so,
1582 the DSMB will must ensure that all investigations, or parts of investigations presenting
1583 that risk, are terminated as soon as possible but no later than 5 working days after the
1584 DSMB will makes this determination and no later than 15 working days after first receipt
1585 notice of the UADE.
- 1586 • In the case of a device system component malfunction (e.g. pump, CGM, control

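### Section 12.1.1 gives no clear reporting route for non-serious, non-device procedure harms and device-stopping events, and one 12.8 exclusion cancels the limit set by another

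*Combined protocol and SAP*

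**What the plan says.** Section 12.1.1 opens with "A reportable adverse event includes any untoward medical occurrence that meets one of the" criteria that follow, and then lists six:

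1. "A Serious Adverse Event as defined in section 12.1.2".
2. An Adverse Device Effect (ADE) under 12.1.4, unless 12.8 excludes it.
3. "An Adverse Event as defined in section 12.1.4 occurring in association with a study" procedure.
4. "An AE as defined in section 12.1.1 which leads to discontinuation of a study device for 2" hours or more.
5. Severe hypoglycemia under 12.3.1.
6. DKA, or a hyperglycemic or ketosis event that meets the criteria in 12.3.2.

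Section 12.1.4, cited by criteria 2 and 3, is headed Adverse Device Effect. It reads "Any untoward medical occurrence in a study participant which the device may have caused or to" which it may have contributed. Section 12.1 contains no separate general definition of an adverse event.

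Section 12.8 requires all device effects, complaints and malfunctions to be reported, apart from eight listed exceptions. The first exception is "Component disconnections", with no condition attached. The sixth is "Intermittent device component disconnections/communication failures not leading to" replacement of the system. The lead-in adds that an excepted issue is still reported as an adverse event if it meets the adverse event criteria.

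**The concern.** Criterion 3 appears to be there to capture harm from study procedures, and criterion 4 to capture events serious enough in practice to take a participant off a device. As cross-referenced, neither clearly does so. Section 10.1.1 warns that blood draws can "include bleeding from the sampling site, formation of a small blood clot or swelling of the vein", and it also names fainting. These are harms of a study procedure in which no device takes part.

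In 12.8, the sixth exception is worded so that a disconnection forcing replacement of the system stays reportable. The first exception removes it again.

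Under 12.3.2, it is the reportable adverse events that must go on the adverse event form. If staff cannot tell from the text whether an event is reportable, two of them may classify the same event differently, and events never recorded are hard to recover afterwards. The protocol describes itself as a significant-risk device study under an IDE, so these are operative safety rules.

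**Working it through.** The plan states no figure on this point and no arithmetic applies. The check is to write the rules as logic and run cases through them.

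**Inputs** (from 12.1.1, 12.1.4, 12.3 and 12.8). Let S = serious; D = possibly caused or contributed to by the device; X = excluded by 12.8; P = associated with a study procedure; T = device stopped for 2 hours or more; G = meets the severe hypoglycemia, hyperglycemia, ketosis or DKA criteria; R = reportable.

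**Rule as written:**

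R = S, or (D and not X), or (P and D), or (T and R), or G.

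The third term has D in it because criterion 3 borrows the ADE definition. The fourth has R in it because criterion 4 refers to its own list.

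**Cases:**

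- *Fainting at a blood draw, non-serious.* P is true; S, D, T and G are false. No term is met, so R is false. If criterion 3 used a general definition, its term would be P alone and R would be true.
- *A non-serious illness unrelated to the device, with the pump or CGM off for 2 hours or more.* Only T is true. The rule reduces to R = R, which both answers satisfy. The text does not decide the case: a strict reader leaves the event out, and a generous reader brings it in.
- *A procedure-associated device effect on the 12.8 list.* D, X and P are true. Criterion 2 fails because of X, but criterion 3 has no 12.8 carve-out, so R is true. Criterion 3 is therefore not empty. Its literal scope is procedure-associated device effects.
- *A serious, qualifying glycemic, or unexcluded device-related event, whatever its link to a procedure or a device stop.* S, G, or (D and not X) is true, so R is true. The wrong references do no damage here.

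**Disconnections under 12.8:**

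| Event | First exception alone | Sixth exception alone | Both, as written |
|---|---|---|---|
| Intermittent disconnection, no replacement, no adverse event | not reported | not reported | not reported |
| Disconnection needing system replacement, no adverse event | not reported | reported | not reported |
| Disconnection with harm meeting the adverse event criteria | reported as an adverse event | reported as an adverse event | reported as an adverse event |

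The second row is the contradiction: the limit in the sixth exception has no effect while the first one stands. One corner stays unclear even then. For a device effect arising from a disconnection, criterion 2 defers to 12.8, and 12.8 refers back to the adverse event criteria.

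**Intent.** Section 12.4 has the investigator class any adverse event as related or unrelated to the device and names intercurrent illness among other causes. Section 12.1.5 says an adverse event can occur without a device complaint. Both presuppose adverse events that are not device effects, so the narrow literal result looks unintended.

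**The case against.** The strongest reply is that no sensible reader would apply these rules so narrowly. The opening verb of 12.1.1 is *includes*, so the list is not stated to be closed. The section is headed Adverse Events and its opening line speaks of any untoward occurrence, which can serve as the missing definition for criterion 4. Sections 12.1.5 and 12.4 point the same way. Collection is broad: section 5.1.1 asks participants to call about any health problem, and Visits 3 to 6 ask about adverse events, device effects and device issues. Some procedure harms would also count as serious under the investigator-judgment item in 12.1.2.

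Most of this stands, and it limits the point. It makes criterion 4 indeterminate rather than void. It does not repair criterion 3, which names a section that defines something else. Asking broadly at visits also does not settle which answers must be reported.

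Three stronger readings are tempting, and the documents do not support them:

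- *That procedure harms, device-stopping events and disconnections are unreportable as whole classes.* Criteria 1, 2, 5 and 6 still catch the serious, unexcluded device-related and qualifying glycemic events. The 12.8 lead-in keeps excepted issues reportable as adverse events where those criteria are met.
- *That criteria 3 and 4 can never add an event.* Criterion 3 can add a procedure-associated device effect that 12.8 excludes, and criterion 4 admits a generous reading.
- *That the suspension rule in 12.11.2 or the DSMB's device record is compromised.* Section 12.11.2 acts on malfunctions that result in severe hypoglycemia or severe hyperglycemia; harms meeting 12.3.1 or 12.3.2 are reportable under criteria 5 and 6. The protocol says adverse events go to the DSMB and leaves further detail to a separate charter. It does not say that device-issue reports go there.

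**Conclusion.** Wrong as written, within narrow limits. Read literally, criterion 3 adds no procedure harm without device involvement, and the scope of criterion 4 is indeterminate. Procedure harms and device-stopping events that are non-serious, non-device and non-glycemic therefore lack a clear reporting route. Separately, a disconnection that needs system replacement but causes no adverse event is not reported as a device issue, despite the limit in the sixth exception of 12.8.

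In size, this is two of six criteria in 12.1.1 with faulty references and one pair of conflicting bullets among eight in 12.8. The number of events affected cannot be derived from the documents. Sample size, alpha, power and the primary analysis are not touched. The conclusion assumes that staff apply the written cross-references, and that no document outside this protocol, such as a form-completion guide, supplies the missing definition. The edits change what gets reported, so they should be made.

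**What to change.** 1. Open 12.1.1 with a general definition: an adverse event is any untoward medical event in a participant, whether or not it is related to a study device.
2. In criterion 3, replace the reference to 12.1.4 with a reference to that definition. In criterion 4, replace the self-reference in the same way. Criterion 2 keeps its reference to 12.1.4.
3. In 12.8, delete the stand-alone first exception and keep the sixth, with its limit to disconnections and communication failures that do not end in system replacement.

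The cost is a short wording amendment and, from then on, a few more adverse event and device-issue forms. Nothing in the design or analysis changes.

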1587 algorithm), information will be forwarded to the responsible manufacturer by the study
1588 personnel.

1589 **12.10. Data and Safety Monitoring Board**

1590 An independent Data and Safety Monitoring Board (DSMB) will be establish to review compiled
1591 safety data at periodic intervals to oversee and monitor our randomized clinical trial to ensure
1592 the safety of participants, as well as the validity and integrity of the data.

1593 Details regarding membership, meetings, responsibilities will be documented in a separate DSMB
1594 Charter.

CLINICAL PROTOCOL

1595 **12.11. Stopping Criteria**

1596 **12.11.1. Participant Discontinuation**

1597 Rules for discontinuing study device use are:

- 1598 • The investigator believes it is unsafe for the participant to continue on the intervention.
1599 This could be due to the development of a new medical condition or worsening of an
1600 existing condition; or participant behavior contrary to the indications for use of the device
1601 that imposes on the participant's safety
- 1602 • The participant requests that the treatment be stopped
- 1603 • Two distinct episodes of DKA
- 1604 • Two distinct severe hypoglycemia events as defined in section 12.3.1

1605 **12.11.2. Suspending/Stopping Overall Study**

1606 In the case of an unanticipated system malfunction resulting in a severe hypoglycemia or severe
1607 hyperglycemia event, use of the study device system will be suspended while the problem is
1608 diagnosed.

1609 In addition, study activities could be similarly suspended if the manufacturer of any constituent
1610 study device requires stoppage of device use for safety reasons (e.g. product recall). The affected
1611 study activities may resume if the underlying problem can be corrected by a protocol or system
1612 modification that will not invalidate the results obtained prior to suspension.

1613 **12.12. Independent Safety Oversight**

1614 A Medical Monitor will review all DKA and severe hypoglycemia irrespective of relatedness to
1615 study device use, and all serious events (including UADEs) related to study device use at the time
1616 of occurrence. The Medical Monitor can request modifications to the study protocol or
1617 suspension or outright stoppage of the study if deemed necessary based on the totality of safety
1618 data available. Details regarding Medical Monitor review will be documented in a separate
1619 Medical Monitor document.

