1620 **Chapter 13 Miscellaneous Considerations**

1621 **13.1. Prohibited Medications, Treatments, and Procedures**

1622 Participants using glulisine at the time of enrollment will be asked to contact their personal
1623 physician to change their prescribed personal insulin to lispro or aspart for the duration of the
1624 trial.

1625 The study devices (study insulin pump, study CGM) must be removed before Magnetic Resonance
1626 Imaging (MRI), Computed Tomography (CT) or diathermy treatment. Participants may continue
1627 in the trial after temporarily discontinuing use if requiring one of the treatments above.

1628 **13.2. Participant Withdrawal**

1629 Participation in the study is voluntary. Participant may withdraw at any time. For participants
1630 who do withdraw from the study, the study team will determine if their data will be used in
1631 analysis.

1632 **13.3. Confidentiality**

1633 For security and confidentiality purposes, subjects will be assigned an identifier that will be used
1634 instead of their name. Protected health information gathered for this study may be shared with
1635 the third-party collaborators. De-identified subject information may also be provided to
1636 collaborators involved in the study after the appropriate research agreement has been executed.

1637 **Chapter 14 Statistical Consideration**

1638 **14.1. Design and Randomization**

1639 This is a randomized crossover study in T1DM designed to demonstrate the efficacy of
1640 personalized feedback (PF) and decision support (DSS) over sensor-augmented pump (SAM)
1641 therapy and to establish relationships between the level of glucose variability (GV) control
1642 achievable by the intervention and individual psycho-behavioral characteristics.

1643 We plan to split the study into 4 cohorts of about 25 participants each (expected retention 20
1644 per cohort). Each cohort will continue for ~7 months and will have the structure presented in
1645 Figure 5. Following recruitment, screening, and a run-in period of SAM, participants will be
1646 randomized into one of two groups: escalation vs. de-escalation of devices and function. Each
1647 treatment modality (SAM, PF, DSS) will continue for about 8 weeks, with the last 4 weeks used
1648 to assess GV from CGM data.

1649 **Escalation: SAM → PF → DSS**

1650 **De-escalation: DSS → PF → SAM**

1651 **14.2. Sample Size**

1652 **14.2.1. Sample Size Determination:**

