1653 Sample size determination is based on our related pilot studies of DSS. We estimate that the
1654 effect size of DSS vs. SAM will be $f^2=0.22$. Power calculations (G*Power 3.1.9.2) assuming $\alpha=0.017$
1655 (corrected for multiple comparisons), 95% power, correlation of 0.55 between the repeated
1656 measures, and attrition of 20%, yield a sample size of N=100 subjects to be randomized at
1657 baseline, with N=80 subjects completing the study. PF vs. SAM assumes the same effect size. We
1658 expect that while overall DSS effect vs. PF will be smaller than vs. SAM, GV control over time will
1659 be more consistent. Aim 1.3 analysis therefore assumes a small effect size (0.15) but 5 repeated
1660 measures (bi-weekly) in each condition with higher correlation (0.65), leading to an achieved
1661 power of 97.2% for this Aim.

1662 **14.2.2. Exploration of the effect of treatment escalation vs. de-escalation:**

1663 A key advantage of the proposed study design (beyond the optimal statistical power) is the
1664 possibility to explore the glucose control and psycho-behavioral impact of features being added
1665 and/or enhanced with prescriptive components (DSS), vs. features being limited to information
1666 (PF) or even removed (SAM). We will perform this analysis by looking at the between factors in
1667 the repeated ANOVA analysis, contrasting the escalation group vs. de-escalation group. While

CLINICAL PROTOCOL

1668 not powered, this analysis will provide key insights in the future feature adaptation schemes
1669 based on the ATI.

1670 **14.3. Outcome Measures**

1671 **14.3.1. Glycemic outcomes:**

1672 The primary outcome of this study will be Glucose Variability (GV) as measured by CGM-based
1673 Coefficient of Variation (CV), as recommended by the International Consensus on Use of
1674 Continuous Glucose Monitoring. To further characterize glucose control, we will compute other
1675 CGM Consensus outcomes as well:

- 1676 • Average
- 1677 • Percent in different ranges:
 - 1678 ○ <50 mg/dL
 - 1679 ○ <54 mg/dL
 - 1680 ○ <60 mg/dL
 - 1681 ○ <70 mg/dL
 - 1682 ○ ≤70-≤180 mg/dL
 - 1683 ○ >180 mg/dL
 - 1684 ○ >250 mg/dL
 - 1685 ○ >300 mg/dL
- 1686 • SD and coefficient of variation
- 1687 • LBGI, HBGI, ADRR

1688 Each modality of treatment will be assessed using the last 4 weeks of CGM recordings, as we
1689 expect most of the GV benefits of each intervention to be realized within the first 4 weeks of the

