1690 intervention, and a minimum of 24 days of data is considered optimal for CGM-based CV
1691 determination.

1692 **14.3.2. Glucose Variability Reduction Achieved with CGM-based expert systems:**

1693 General linear models (GLM) (repeated measures ANOVA) will be used to assess the significance
1694 of the differences in average response between SAM, PF, and DSS across appropriate CGM-based
1695 metrics. The particular design of the clinical study allow for Aims 1.1, 1.2, and 1.3 to each be
1696 addressed independently in a randomized crossover analysis, as shown in Figure 4. While the
1697 randomized order of the interventions (escalation vs de-escalation) allows for an objective
1698 assessment of the average efficacy of each of them, we will introduce the order as a fixed factor
1699 to verify if significant study effects can be detected. Finally, we will study the evolution of GV
1700 within each modality period: GV and other CGM-based outcomes will be computed bi-weekly
1701 (the minimum length of time for precise GV assessment) and entered in a repeated measures

CLINICAL PROTOCOL

1702 GLM analysis; within-subject contrast (linear and polynomial) using 5 repeated measures per
1703 condition to explore the evolution of the glycemic outcomes in time; Aim 1.3.

1704 **14.4. Exploration of the effect of treatment escalation vs. de-escalation**

1705 A key advantage of the proposed study design (beyond the optimal statistical power) is the
1706 possibility to explore the glucose control and psycho-behavioral impact of features being added
1707 and/or enhanced with prescriptive components (DSS), vs. features being limited to information
1708 (PF) or even removed (SAM). We will perform this analysis by looking at the between factors in
1709 the repeated ANOVA analysis, contrasting the escalation group vs. de-escalation group. While
1710 not powered, this analysis will provide key insights in the future feature adaptation schemes
1711 based on the ATI.

1712 **14.5. Psychological and Behavioral Questionnaires**

1713 *Quantitative* data on usability and satisfaction will be analyzed using simple descriptive statistics.
1714 In addition, we will analyze scores from the measures in the psychosocial assessment battery to
1715 determine if changes occur over time and between groups. Using SPSS 26, we will construct
1716 predictive models in the general linear modeling (GLM) framework to examine each set of

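### Section 13.2 lets the study team choose, with no rule or timing, whether withdrawn participants' data are analysed, although 20% attrition is planned

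*Combined protocol and SAP*

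**What the plan says.** Section 13.2 allows withdrawal at any time and adds that, for participants "who do withdraw from the study, the study team will determine if their data will be used in" analysis. That is the whole rule.

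The surrounding text:

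- **Section 14.2.1** plans for losses: "measures, and attrition of 20%, yield a sample size of N=100 subjects to be randomized at" baseline, with 80 completing.
- **Section 14.3.2** names the method: "General linear models (GLM) (repeated measures ANOVA) will be used to assess the significance" of differences between SAM, PF and DSS. It says Aims 1.1, 1.2 and 1.3 are each "addressed independently in a randomized crossover analysis, as shown in Figure 4. While the" (the figure is not available in the text reviewed).
- **Section 14.3.1** defines the outcome window: "Each modality of treatment will be assessed using the last 4 weeks of CGM recordings, as we" expect most benefit to appear earlier in the phase. It calls 24 days of data optimal.
- **Section 14.6** names all randomized participants, but only for the baseline table. No analysis set or missing-data rule is given for the glycemic outcomes.
- **Section 12.10** gives the DSMB a remit covering "the safety of participants, as well as the validity and integrity of the data", but no stated role in choosing the analysed data.
- **Section 1.1.1** describes CGM data reaching the study server in real time. No masking is described anywhere.

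**The concern.** The people who can see the outcome data may decide afterwards whose data count, and no later analysis could show that the choice was neutral. A reader of the results could not tell whether they describe 80 participants, 100, or something between.

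Two problems need to be kept apart. The first is the discretion itself, which comes from 13.2. The second is leaving that depends on outcome, which affects any analysis restricted to completers, whoever chooses the set. Repeated-measures ANOVA conventionally drops anyone without a value for a required phase, so completers are the likely default. That is inferred from the method and is not written in 14.3.2.

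**Working it through.** **Plan's own figure.** For a within-subject F test, λ = f²·N·m/(1−ρ). With f = 0.22, m = 2, ρ = 0.55, α = 0.017 and N = 80, power is 95.4%; 79 participants suffice for 95%, and 80/(1−0.20) = 100. This reproduces 14.2.1 if 0.22 is read as f (the text writes f²). Power is 97.4% at N = 90 and 98.6% at N = 100. Losing all 20 is already allowed for, so the issue is selection and not power.

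**Where the discretion can act.** Escalation runs SAM, PF, DSS; de-escalation runs DSS, PF, SAM.

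- Anyone leaving before the Phase 3 window has no DSS-SAM pair, so including them cannot move that contrast in a paired analysis.
- An escalation participant leaving after Phase 2 has a PF-SAM pair. A de-escalation participant leaving then has a DSS-PF pair. These count only if the aims are run pairwise.
- Someone leaving during or near the Phase 3 window could supply a DSS-SAM pair, because the final four weeks of recordings are not tied to scheduled weeks.

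**Size of the discretion, PF vs SAM.** Assumptions: 80 completers, no true effect, two-sided α = 0.017 (critical z = 2.387), and differences standardized to SD 1. Keeping the best j of n usable leavers shifts z by roughly S/√(80+j), where S is the expected sum of the top j of n normal order statistics.

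- Best 2 of 5: S = 1.66, shift 1.66/√82 = 0.18; error ≈ Φ(−2.20) + Φ(−2.57) = 1.4% + 0.5% = 1.9% (simulated 1.8%).
- Best 5 of 10: S = 3.69, shift 3.69/√85 = 0.40; error ≈ Φ(−1.99) + Φ(−2.79) = 2.3% + 0.3% = 2.6% (simulated 2.5%; 2.3% with sequence as a factor). This is an upper-end case in which all 10 escalation leavers finish Phase 2.
- All or none, fixed beforehand: 1.7%. Chosen after seeing results, 10 leavers: about 2.3% (simulated).
- Number kept also free, 10 leavers: false positives in the favourable direction rise from about 0.8% to 2.5% (simulated).

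**Outcome-related leaving, completers, DSS vs SAM.** Assume the 20% with the highest latent leaving score drop out in each sequence, and the score correlates r with the DSS-SAM difference. In phase-SD units, SD of the difference = √(2(1−0.55)) = 0.949. The mean shift among the 80% who stay = r × φ(0.842)/0.8 × 0.949 = r × 0.350 × 0.949 = 0.332r. The standard error = 0.949/√80 = 0.106.

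| r | Bias (phase SD) | Bias/SE | Type I, approximate | Type I, simulated |
|---|---|---|---|---|
| 0.1 | 0.03 | 0.31 | 2.3% | 2.3% |
| 0.2 | 0.07 | 0.63 | 4.0% | 3.9% |
| 0.3 | 0.10 | 0.94 | 7.4% | 7.2% |

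That is for leaving in the same direction in both sequences. With one sequence only, the bias halves and the error is about 1.8% to 3.2%. In opposite directions it stays at 1.7-1.9%.

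**What a mixed model on all available phases does.** In the same-direction case the error falls to 1.9-2.0%, 2.7-3.1% and 3.7-4.8%. The variance relative to 80 completers (40 per sequence plus 10 leavers per sequence, compound symmetry 0.55, linear period) is:

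| Leavers contribute | PF vs SAM, DSS vs PF | DSS vs SAM |
|---|---|---|
| Phases 1 and 2 | 0.87 | 0.93 |
| Half each | 0.92 | 0.94 |
| Phase 1 only | 0.98 | 0.95 |

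**The case against.** **The discretion is nearly inert.** The mid-range case is 1.8% against 1.7%, and if 14.3.2 is run as one three-level ANOVA, participants missing a phase drop out whatever the team decides. This stands as a limit on size. It does not supply the missing rule.

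**Outcome-related leaving does not come from 13.2, and its larger figures need assumed correlations.** Correct on both counts. They are shown as a range and as a separate exposure.

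**Twenty leavers may be too many.** Section 14.2.1 counts 20% after randomization, but section 1.5 applies 80% completion to those recruited, and section 5.3.1 withdraws run-in failures before randomization. With fewer post-randomization leavers, every figure shrinks. This stands.

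**A single sentence in 13.2 would remove the discretion.** True. The model change answers the completer exposure and recovers data already collected.

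Stronger readings that a reader might infer, and that the documents do not support:

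- That 14.3.2 itself excludes incomplete participants. It says nothing on this.
- That the discretion can swing DSS vs SAM generally. It can do so only through someone leaving during or near the Phase 3 window.
- That the PF vs SAM figures carry over to Aim 1.3. That aim includes non-inferiority, uses bi-weekly measures and has no stated margin, so its error inflation was not computed. Only its superiority part can be said to be open to the same effect.
- That the results would be seriously biased. The documents give neither the strength nor the direction of outcome-related leaving.

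**Conclusion.** The point holds, and should be fixed. Section 13.2 leaves the analysed set to unmasked judgement with no rule or timing, and nothing elsewhere limits it. Confidence in that textual gap is high.

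The size is conditional. For PF vs SAM the inflation is small: at most about 2.6% against a nominal 1.7% with a fixed number kept, or 2.5% against 0.8% in the favourable direction with the number free. Both upper figures assume pairwise analysis and 10 usable escalation leavers. The exposure of a completer analysis of DSS vs SAM runs from negligible to material and depends on inputs the plan does not give. Type I errors do not depend on the SD. Biases are left in phase-SD units because the only SDs given for CV come from the 48-hour pilot periods in section 1.1.2.

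**What to change.** **Section 13.2.** Replace the discretion with: *Data collected before withdrawal are included in the analysis unless the participant withdraws permission to use them.*

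**Section 14.3.2.** Make the primary analysis a linear mixed model by assigned sequence, on all randomized participants with at least one evaluable phase, with treatment, sequence and linear period as fixed effects and participant as random effect. Three details matter:

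- Take CGM data from scheduled weeks 5-8 of the phase, so that a mid-phase leaver's early weeks stay out.
- Fix the minimum number of days before outcome review. Fourteen days is one option, since the plan calls two weeks "the minimum length of time for precise GV assessment) and entered in a repeated measures" analysis. Use 24 days as a sensitivity threshold.
- Do not use a three-level period factor. PF is always Phase 2 (sections 6.4 and 7.4), so both PF contrasts would become inestimable.

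Apply the same inclusion rule to the bi-weekly Aim 1.3 analysis. Keep the completer repeated-measures ANOVA as a sensitivity analysis, and add one missing-not-at-random analysis that shifts leavers' missing-phase CV against the advisory mode until the conclusion changes.

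**Cost.** A few sentences and a model type already named in section 1.3.6, with no extra data or participants. The price is slightly more analysis work and reliance on missing-at-random and a linear period trend.
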